## **DOCUMENT HISTORY**

Document	Date of Issue	Overall Rationale
-02	21-JUL-2020	The overall rationale for the amendment is to allow participants who have completed the study to be discontinued and enrolled in a pembrolizumab extension study.
-01	09-NOV-2017	Revisions/updates incorporated based on feedback from regulatory agency and sites.
-00	02-OCT-2017	Original protocol

## **PROTOCOL AMENDMENT SUMMARY OF CHANGES**

### **Amendment -02**

#### **Overall Rationale for the Amendment:**

The overall rationale for the amendment is to allow participants who have completed the study to be discontinued and enrolled in a pembrolizumab extension study.

#### **Summary of Changes Table:**

Section # and Name	Description of Change	Brief Rationale
1 Synopsis 5.1.2 Study Diagram 5.3 Beginning and End of Study Definition 9.1.7 Assignment of Treatment/Randomization Number	Language was added to allow participants who have completed the study to be discontinued and enrolled in a pembrolizumab extension study.	This change will allow this study to be closed.

## 1. Synopsis

Protocol Title:  Phase 1b Open-label Study of MK-7162 in Combination with Pembrolizumab (MK-3475) +/- other therapies in Participants with Advanced Solid Tumors										
Short Title:  Phase 1b MK-7162 in combinations with pembrolizumab (MK-3475) +/- other therapies in participants with advanced solid tumors										
Objectives/Hypotheses and Endpoints:  Male/female participants of at least 18 years of age with advanced/metastatic solid tumors will be enrolled in this trial.										


Objective	Endpoint	

Primary  1. To determine the safety and tolerability and to establish a preliminary recommended Phase 2 dose (RP2D) of MK-7162 administered in combination with pembrolizumab	

• Dose-limiting toxicity (DLT)

• Adverse events (AEs)

• Discontinuation of study treatment due to an AE

	

Secondary  1. To evaluate the pharmacokinetics (PK) of MK-7162 administered orally as monotherapy and in combination with pembrolizumab intravenous (IV) infusion	

• PK parameters, including area under the curve (AUC), minimum observed combination (<math>C_{min}</math>), and maximum observed combination (<math>C_{max}</math>)

	

2. To evaluate pharmacodynamics (PD) of MK-7162 alone and in combination with pembrolizumab through measurement of kynurenine (KYN) and tryptophan (TRP) levels	

• KYN and TRP will be measured as PD biomarkers of Indoleamine-2,3-dioxygenase-1 (IDO1) inhibition

	

3. To evaluate the objective response rate (ORR) to MK-7162 in combination with pembrolizumab	

• ORR based on Response Evaluation Criteria In Solid Tumors version 1.1 (RECIST 1.1) and immune-based RECIST (iRECIST) as assessed by the investigator

	

	Objective	Endpoint	Primary  1. To determine the safety and tolerability and to establish a preliminary recommended Phase 2 dose (RP2D) of MK-7162 administered in combination with pembrolizumab	

• Dose-limiting toxicity (DLT)

• Adverse events (AEs)

• Discontinuation of study treatment due to an AE

	Secondary  1. To evaluate the pharmacokinetics (PK) of MK-7162 administered orally as monotherapy and in combination with pembrolizumab intravenous (IV) infusion	

• PK parameters, including area under the curve (AUC), minimum observed combination (<math>C_{min}</math>), and maximum observed combination (<math>C_{max}</math>)

	2. To evaluate pharmacodynamics (PD) of MK-7162 alone and in combination with pembrolizumab through measurement of kynurenine (KYN) and tryptophan (TRP) levels	

• KYN and TRP will be measured as PD biomarkers of Indoleamine-2,3-dioxygenase-1 (IDO1) inhibition

	3. To evaluate the objective response rate (ORR) to MK-7162 in combination with pembrolizumab	

• ORR based on Response Evaluation Criteria In Solid Tumors version 1.1 (RECIST 1.1) and immune-based RECIST (iRECIST) as assessed by the investigator

Objective	Endpoint									
Primary  1. To determine the safety and tolerability and to establish a preliminary recommended Phase 2 dose (RP2D) of MK-7162 administered in combination with pembrolizumab	

• Dose-limiting toxicity (DLT)

• Adverse events (AEs)

• Discontinuation of study treatment due to an AE

									
Secondary  1. To evaluate the pharmacokinetics (PK) of MK-7162 administered orally as monotherapy and in combination with pembrolizumab intravenous (IV) infusion	

• PK parameters, including area under the curve (AUC), minimum observed combination (<math>C_{min}</math>), and maximum observed combination (<math>C_{max}</math>)

									
2. To evaluate pharmacodynamics (PD) of MK-7162 alone and in combination with pembrolizumab through measurement of kynurenine (KYN) and tryptophan (TRP) levels	

• KYN and TRP will be measured as PD biomarkers of Indoleamine-2,3-dioxygenase-1 (IDO1) inhibition

									
3. To evaluate the objective response rate (ORR) to MK-7162 in combination with pembrolizumab	

• ORR based on Response Evaluation Criteria In Solid Tumors version 1.1 (RECIST 1.1) and immune-based RECIST (iRECIST) as assessed by the investigator

									

**Overall Design:**

Trial Phase	Phase 1b
Clinical Indication	Treatment of participants with advanced solid tumors
Population	Participants with histologically or cytologically confirmed advanced solid tumors by pathology report who have received or been intolerant to all treatment known to confer clinical benefit will be enrolled.
Trial Type	Interventional
Type of Design	This is an open-label, multicenter, nonrandomized dose escalation and confirmation study of MK-7162 in combination with pembrolizumab.
Type of Control	No treatment control
Trial Blinding	Unblinded open-label
Estimated Duration of Trial	The Sponsor estimates that the trial will require approximately 2 years from the time the first participant signs the informed consent until the last participant's last study-related phone call or visit.

**Number of Participants:**

Approximately 40 participants will be enrolled in the dose escalation and confirmation phase of this trial. Enrollment of additional participants in expansion cohorts will be specified in a future protocol amendment.

**Treatment Groups and Duration:**

Treatment Groups	
Participants will be allocated via Interactive voice response system/integrated web response system (IVRS/IWRS) to dose-level cohorts of MK-7162, administered orally (PO). MK-7162 will be administered as monotherapy once a day (QD) every day of each 21-day (3-week) cycle. Starting with treatment Cycle 2 until treatment Cycle 36, participants will receive MK-7162 daily QD in combination with pembrolizumab 200 mg IV every 3 weeks. Each treatment cycle is 3 weeks.
 
The study will follow the modified toxicity probability interval (mTPI) method (Section 5.5.3.1) to identify a preliminary RP2D, maximum tolerated dose (MTD) and/or maximum administered dose (MAD) of MK-7162 in combination with pembrolizumab. The dose limiting toxicity (DLT) evaluation period will be 2 cycles (6 weeks/42 days).
 
Upon identification of the preliminary RP2D of MK-7162 for use in combination with pembrolizumab, additional participants with solid tumors will be enrolled in the dose expansion phase of this trial. Participants in the expansion phase of this trial will receive MK-7162 in combination with pembrolizumab as dual therapy or in combination with additional chemotherapeutic or immune-modulatory agents. The dose expansion phase of this trial will be initiated through an amendment to this protocol.

Duration of Participation	
The participant duration in the trial is approximately 2 years from the time the participant signs the Informed Consent Form (ICF) through the final contact.
 
After a screening phase of up to 28 days, each participant will receive assigned treatment for up to 36 treatment cycles (approximately 2 years). Treatment may continue until 1 of the following occurs: disease progression, unacceptable AEs, intercurrent illness that prevents further administration of treatment, investigator decision to withdraw the participant, participant withdraws consent, pregnancy of the participant, noncompliance with trials treatment or procedure requirements, or administrative reasons requiring cessation of treatment.
 
After the end of treatment, each participant will be followed for the occurrence of AEs and spontaneously reported pregnancy as described in Section 9.3.
 
Once the participant has achieved the study objective or the study has ended, the participant will be discontinued from this study and may be enrolled in an extension study to continue protocol-defined assessments and treatment.

A list of abbreviations used in this document can be found in Appendix 1.

## 2. Schedule of Activities (SoA)

### 2.1 Dose Escalation and Confirmation

Trial Phase:	Screening	Treatment (Treatment Cycle = 21 days)								End of Treatment (EoT)	Post-treatment		Notes	
		MK-7162 Mono-therapy		MK-7162 and Pembrolizumab Combination Therapy							Safety Follow-up	Survival Follow-up		
Visit or Cycle (C):		C1		C2		C3		C4	C5 thru C36	Last Dose / Discontinuation	30 days after the last dose	Every 12 weeks after the last dose		
		D1	D15	D1	D15	D1	D15	D1	D1					
Schedule Window (Days):	-28 to -1		± 3	± 3	± 3	± 3	± 5	± 3	± 3	± 7	± 7	± 14		
Administrative Procedures														
Informed Consent Form (ICF)	X												• Written consent must be obtained prior to performing any protocol-specific procedures. • An ICF signed >28 days prior to C1D1 does not need to be replaced.	
Informed Consent for Future Biomedical Research (FBR) (optional)	X													
Participant Identification Card	X													
Inclusion/Exclusion Criteria	X													
Demographics and Medical History	X													
Prior Medication and Concomitant Medication Review	X	X		X		X		X	X	X	X			

Trial Phase:	Screening	Treatment (Treatment Cycle = 21 days)								End of Treatment (EoT)	Post-treatment		Notes	
		MK-7162 Mono-therapy		MK-7162 and Pembrolizumab Combination Therapy							Last Dose / Discontinuation	Safety Follow-up	Survival Follow-up	
		C1		C2		C3		C4	C5 thru C36		30 days after the last dose	Every 12 weeks after the last dose		
Visit or Cycle (C):		D1	D15	D1	D15	D1	D15	D1	D1					
Scheduling Day (D):		-28 to -1		± 3	± 3	± 3	± 3	± 5	± 3	± 3	± 7	± 7	± 14	
Disease Details and Prior Oncology Treatment History	X													
MK-7162 Administration and Dispensing		X		X		X		X	X				
 
Participants are to be dosed within 3 days of allocation.
 
All treatment visits should follow an overnight fast. Some PK and PD samples must be obtained in the morning prior to administration of a morning dose of MK-7162.
 
 
C1D1: Minimum 8-hour observation period following initial MK-7162 monotherapy dose on C1D1
 
C2D1-C36D1: For pembrolizumab combination treatment day visits, MK-7162 should be administered in clinic a minimum of 1 h prior to initiation of pembrolizumab infusion.
	
Pembrolizumab Administration				X		X		X	X				
C2D1: Minimum 8-hour observation period following completion of pembrolizumab infusion
	
New Anticancer Therapy Status											X	X		

Trial Phase:	Screening	Treatment (Treatment Cycle = 21 days)							End of Treatment (EoT)	Post-treatment		Notes	
		MK-7162 Mono-therapy		MK-7162 and Pembrolizumab Combination Therapy						Last Dose / Discontinuation	Safety Follow-up		
Visit or Cycle (C):		C1		C2		C3		C4	C5 thru C36	30 days after the last dose	Every 12 weeks after the last dose		
Scheduling Day (D):		D1	D15	D1	D15	D1	D15	D1	D1				
Schedule Window (Days):	-28 to -1		± 3	± 3	± 3	± 3	± 5	± 3	± 3	± 7	± 7	± 14	
Survival Status		← ----- →									X	Treatment and Safety Follow-up Phase: Upon Sponsor request, participants may be contacted for survival status at any time during the course of the study Survival Follow-up Phase: After Investigator determined PD or start of new anticancer treatment.	
Efficacy Procedures													
Tumor Imaging: RECIST 1.1 and iRECIST Response Assessment	X							X	X	X			
 
• Imaging obtained via CT, PET/CT, or MRI.
 
• Medical Photography for cutaneous lesions: Obtained on the same schedule as imaging
 
• On-treatment visit window: ± 7 days
 
 Screening Visit: Baseline tumor imaging and/or medical photography for cutaneous lesions should be performed within 28 days prior to first dose of MK-7162. Treatment Phase: Obtain first on-treatment imaging at Week 9 (C4D1); Obtain subsequent imaging every 9 weeks thereafter.
Medical Photography (cutaneous lesions)	X							X	X	X			
Safety Assessments and Procedures													
AE/SAE Review	X	X ← ----- → X							X	X			
Full Physical Examination	X								X	X			
Directed Physical Examination		X		X		X		X	X				

Trial Phase:	Screening	Treatment (Treatment Cycle = 21 days)								End of Treatment (EoT)	Post-treatment			
		MK-7162 Mono-therapy		MK-7162 and Pembrolizumab Combination Therapy							Last Dose / Discontinuation	Safety Follow-up	Survival Follow-up	
		C1		C2		C3		C4	C5 thru C36		30 days after the last dose	Every 12 weeks after the last dose		
Scheduling Day (D):		D1	D15	D1	D15	D1	D15	D1	D1					Notes
Schedule Window (Days):	-28 to -1			± 3	± 3	± 3	± 5	± 3	± 3	± 7	± 7	± 14		
Height	X													
Weight	X	X		X		X		X	X	X				
Vital Signs	X	X		X		X		X	X	X	X			
Consists of temperature, pulse, respiratory rate, blood pressure, and oxygen (O2) saturation.
 
C1D1: Predose: Obtain within 1 h (± 30 min) prior to MK-7162 dose; Postdose: Obtain 2, 4, 6, and 8 h (± 30 min) after dosing
 
C2D1: Predose: Obtain within 1 hour (± 30 min) prior to MK-7162 dose; Postdose: Obtain 2, 4, 6, and 8 h (± 30 min) after completion of MK-7162 and pembrolizumab dosing
 
C3D1 and beyond: Predose: Obtain within 1 h (± 30 min) prior to MK-7162 dose.

12-lead ECG	X	X		X						X				
C1D1 Postdose: Obtain within 30 min after dosing
 
C2D1 Postdose: Obtain within 30 min after the end of the pembrolizumab infusion

Eastern Cooperative Oncology Group (ECOG) Status	X	X		X		X		X	X	X	X			Assessment to confirm eligibility must be performed within 7 days prior to C1D1 dosing

Trial Phase:	Screening	Treatment (Treatment Cycle = 21 days)							End of Treatment (EoT)	Post-treatment		Notes
		MK-7162 Mono-therapy		MK-7162 and Pembrolizumab Combination Therapy						Last Dose / Discontinuation	Safety Follow-up	
Visit or Cycle (C):	C1		C2		C3		C4	C5 thru C36	30 days after the last dose	Every 12 weeks after the last dose		
Scheduling Day (D):	D1	D15	D1	D15	D1	D15	D1	D1				
Schedule Window (Days):	-28 to -1		± 3	± 3	± 3	± 5	± 3	± 3	± 7	± 7	± 14	
Safety: Local Laboratory Evaluations												

Screening: Obtain and evaluate clinical laboratory tests within 7 days prior to first dose of study medication (C1D1) unless otherwise specified. Tests performed prior to the participant signing IC as part of routine clinical management are acceptable in lieu of a screening test, if the test is performed within the specified time frame.
 
Day 1 for All Treatment Cycles: Obtain samples prior to MK-7162 and pembrolizumab dosing, unless otherwise specified
 
See Procedures Manual for details regarding collection and management of samples
												
HIV, Hepatitis B and C screen	X											Historical results are acceptable unless testing is required by local regulation. Tests performed during the 28 day screening period are acceptable.
Hematology	X	X		X		X		X	X	X	X	
Urinalysis	X	X		X		X		X		X		
Comprehensive Chemistry Panel	X	X		X		X		X	X	X		
Lipase and Amylase	X									X		
LDH, GGT	X	X		X		X		X	X			
PT/INR and PTT/aPTT	X			X		X		X	X			Consider ongoing testing for participants on routine warfarin treatment.
Thyroid Function (T3, T4, TSH)	X	X			X			X		X		Tests performed during the 28-day screening period are acceptable for eligibility assessment. Treatment Cycles: Obtain every other treatment cycle, starting with C1: C1, C3, C5, etc.; Obtain at 30-day Safety Follow-up

Trial Phase:	Screening	Treatment (Treatment Cycle = 21 days)								End of Treatment (EoT)	Post-treatment		Notes
		MK-7162 Mono-therapy		MK-7162 and Pembrolizumab Combination Therapy							Last Dose / Discontinuation	Safety Follow-up	Survival Follow-up
Visit or Cycle (C):		C1		C2		C3		C4	C5 thru C36				
		D1	D15	D1	D15	D1	D15	D1	D1				
Schedule Window (Days):	-28 to -1		± 3	± 3	± 3	± 3	± 5	± 3	± 3	± 7	± 7	± 14	
Tumor Markers	X	X		X		X		X	X				Obtain as clinically appropriate (eg, CEA, CA-125, CA-19-9, alpha fetoprotein, etc.)
Pregnancy Test: Serum β-Human Chorionic Gonadotropin (β-hCG) or Urine Test	X									X	X		
 
For women of childbearing potential (WOCBP) only
 
Additional urine/serum testing may be performed if clinically warranted, and/or as defined by local regulations.
 
If a urine pregnancy test cannot be confirmed as negative, a serum pregnancy test is required.
 
Obtain urine pregnancy test within 72 hours prior to the first MK-7162 dose
 

C1D1: Obtain samples predose MK-7162 C2D1 thru C36D1: Predose = prior to MK-7162 administration and prior to pembrolizumab infusion; Postdose = subsequent to MK-7162 administration and pembrolizumab infusion See Procedures Manual for collection and management of samples													
Blood (DNA) for Genetic Analysis		X											Obtain predose
Peripheral Blood Mononuclear Cell	X			X		X	X	X	X	X	X		Screening: Obtain predose on the same day as the Screening tumor biopsy C2D1: Obtain predose on the same day as the tumor biopsy C3D15: Obtain predose on the same day as the tumor biopsy C3D1-C36D1: Predose

Trial Phase:	Screening	Treatment (Treatment Cycle = 21 days)								End of Treatment (EoT)	Post-treatment		Notes
		MK-7162 Mono-therapy		MK-7162 and Pembrolizumab Combination Therapy							Last Dose / Discontinuation	Safety Follow-up	Survival Follow-up
Visit or Cycle (C):		C1		C2		C3		C4	C5 thru C36	30 days after the last dose	Every 12 weeks after the last dose		
Scheduling Day (D):		D1	D15	D1	D15	D1	D15	D1	D1				
Schedule Window (Days):	-28 to -1		± 3	± 3	± 3	± 3	± 5	± 3	± 3	± 7	± 7	± 14	
Plasma for MK-7162 Pharmacokinetics (PK)		X	X	X	X	X	X	X	X	X	X		C1D1 & C1D15: Predose: Obtain following an overnight fast. Postdose: 1, 2, 4, and 8 hrs. Participant to remain fasting for 1 hr subsequent to dosing. C2D1: Predose: Obtain following an overnight fast. Obtain same day as tumor biopsy. C2D15: Predose: Obtain following an overnight fast. C3D1: Predose: Obtain following an overnight fast. Postdose: 1, 2, 4, and 8 hrs. Participant to remain fasting for 1 hr subsequent to MK-7162 dosing. C3D15: Predose: Obtain following an overnight fast. Obtain on the same day as tumor biopsy. C4D1-C36D1: Predose every 4 cycles: C4, C8, C12, etc. Obtain following an overnight fast. Collection time point windows: 1 hr. (± 15 min), 2-8 hrs. (± 30 min)
Serum for Pembrolizumab Pharmacokinetics (PK)				X		X		X	X	X	X		C2D1: Predose; Postdose: 0.5 hrs. (± 5 min) following completion of pembrolizumab infusion C3D1: Predose C4D1-C36D1: Obtain predose every 4 cycles: C4, C8, C12, etc.

Trial Phase:	Screening	Treatment (Treatment Cycle = 21 days)								End of Treatment (EoT)	Post-treatment		Notes	
		MK-7162 Mono-therapy		MK-7162 and Pembrolizumab Combination Therapy							Safety Follow-up	Survival Follow-up		
		C1		C2		C3		C4	C5 thru C36		30 days after the last dose	Every 12 weeks after the last dose		
Scheduling Day (D):		D1	D15	D1	D15	D1	D15	D1	D1					
Schedule Window (Days):	-28 to -1			± 3	± 3	± 3	± 5	± 3	± 3	± 7	± 7	± 14		
Serum for Anti-pembrolizumab Antibodies				X		X		X	X	X	X		C2D1 and C3D1: Predose C4D1-C36D1: Obtain predose every 4 cycles: C4, C8, C12, etc.	
Blood for Plasma Pharmacodynamic (PD) and Biomarker Analyses	X	X	X	X		X	X						Screening: Obtain on the same day as the Screening tumor biopsy. Obtain following an overnight fast. C1D1 & C1D15: Predose: Obtained following an overnight fast. Postdose: 1, 2, 4, and 8 hrs. C2D1: Predose: Obtain following an overnight fast. Obtain on the same day as tumor biopsy. C3D1: Predose: Obtained following an overnight fast. Postdose: 1, 2, 4, and 8 hrs. C3D15: Predose: Obtain following an overnight fast. Obtain the same day as tumor biopsy. Collection timepoint windows: 1 hr. (± 15 min), 2-8 hrs. (± 30 min)	
Whole Blood for Immune profiling	X	X		X		X		X					Obtain during Screening Treatment Cycles: Obtain predose on C1D1, C2D1, C3D1, and C4D1	
Blood for Serum Biomarker Analysis		X		X		X		X	X	X			Treatment Cycles: Obtain predose on D1 of every Cycle.	
Blood for RNA Analysis		X		X		X		X		X			Treatment Cycles: Obtain predose C1D1, C2D1, C3D1, and C6D1 only	

Trial Phase:	Screening	Treatment (Treatment Cycle = 21 days)							End of Treatment (EoT)	Post-treatment		Notes	
		MK-7162 Mono-therapy		MK-7162 and Pembrolizumab Combination Therapy						Last Dose / Discontinuation	Safety Follow-up		
		C1		C2		C3		C4	C5 thru C36		30 days after the last dose	Every 12 weeks after the last dose	
Scheduling Day (D):		D1	D15	D1	D15	D1	D15	D1	D1				
Schedule Window (Days):	-28 to -1		± 3	± 3	± 3	± 3	± 5	± 3	± 3	± 7	± 7	± 14	
Tumor Tissue Collection													
Archival Tumor Tissue	X												Archival tumor tissue is preferred. If archival tumor tissue is unavailable, freshly obtained biopsy tissue may be used (See Procedures Manual for details).
Tumor Biopsy	X												Collection of a newly biopsied tumor tissue specimen is required during screening prior to C1D1 dosing. Must be collected after overnight fast.
Tumor Biopsy				X			X						
 
Initial requirement: C2D1 = mandatory and C3D15 = optional
 
Upon site notification by Sponsor: C2D1 = optional and C3D15 = mandatory
 
All biopsies must be collected after an overnight fast and prior to administration of either MK-7162 or pembrolizumab on the day of the biopsy.
 
 C2D1: Obtain biopsy predose C3D15: Obtain biopsy predose (after 5 additional weeks of MK-7162 in combination with pembrolizumab following C2D1).

Abbreviations: AE = adverse event; CT = computed tomography; DNA = deoxyribonucleic acid; ECG = electrocardiogram; GGT = gamma glutamyl transferase; HIV = human immunodeficiency virus; LDH = lactate dehydrogenase; MRI = magnetic resonance imaging; PET = positron emission tomography; PT/INR = prothrombin time/international normalized ratio; PTT/aPTT = partial thromboplastin time/activated partial thromboplastin time; RECIST 1.1 = Response Evaluation Criteria In Solid Tumors version 1.1; iRECIST = immune-based RECIST; RNA = ribonucleic acid; SAE = serious adverse event; T3 = total triiodothyronine; T4 = total thyroxine; TSH = thyroid stimulating hormone.

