Participants may receive study medication for up to 36 cycles. Participants will be treated until progressive disease, unacceptable toxicity, intercurrent illness that prevents further administration of treatment, Investigator's decision to withdraw treatment, participant withdrawal of consent, pregnancy of the participant, noncompliance with study medication or procedure requirements, participant completes treatment, or administrative reasons requiring cessation of treatment, at which point they will be discontinued from the study.

All participants will be followed for at least 30 days after their last dose of MK-7162 for AE monitoring. Serious adverse events will be collected for 90 days after discontinuation, 30 days if the participant initiates new anticancer therapy less than 30 days after study treatment discontinuation, or the day new anticancer therapy is initiated if between 30 days and 90 days after study treatment discontinuation. Participants with an ongoing AE of Grade  $> 1$  at the time of treatment discontinuation will be followed until resolution of the AE to Grade 0-1, until considered stable by the treating physician, or until beginning a new anticancer therapy, whichever occurs first.

Participants who discontinue treatment for reasons other than confirmed progressive disease will have post-treatment follow-up for disease status (including imaging) until disease progression, initiating a new anticancer therapy, withdrawing consent for study participation, or becoming lost to follow-up.

After confirmed disease progression, each participant who discontinues treatment will be contacted by telephone every 12 weeks ( $\pm 14$  days) for survival until withdrawal of consent to participate in the study, becoming lost to follow-up, death, or end of the study, whichever occurs first.

Specific procedures to be performed during the trial, as well as their prescribed times and associated visit windows, are outlined in the Trial SoA - Section 2. Details of each procedure are provided in Section 9 – Study Assessments and Procedures.

This trial will use an adaptive design based on prespecified criteria. Interim analyses will be conducted to examine clinical trial data on a continuous basis to allow for dose-finding decisions, safety, tolerability, and efficacy analysis.

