#### 9.3.1 Time Period and Frequency for Collecting AE, SAE and Other Reportable Safety Event Information

All AEs, SAEs and other reportable safety events that occur after the consent form is signed but before treatment allocation/randomization must be reported by the investigator if the participant is receiving placebo run-in or other run-in treatment, if the event causes the participant to be excluded from the trial, or is the result of a protocol-specified intervention, including but not limited to washout or discontinuation of usual therapy, diet, or a procedure.

From the time of treatment allocation/randomization through 14 days following cessation of treatment, all AEs, SAEs and other reportable safety events must be reported by the investigator.

Additionally, any SAE brought to the attention of an investigator at any time outside of the time period specified in the previous paragraph must be reported immediately to the Sponsor if the event is considered to be drug-related.

Investigators are not obligated to actively seek AE or SAE or other reportable safety events in former study participants. However, if the investigator learns of any SAE, including a death, at any time after a participant has been discharged from the study, and he/she considers the event to be reasonably related to the study treatment or study participation, the investigator must promptly notify the sponsor.

All initial and follow-up AEs, SAEs and other reportable safety events will be recorded and reported to the sponsor or designee within the timeframes as indicated in [Table 8](#).

Table 8 Reporting Time Periods and Timeframes for Adverse Events and Other Reportable Safety Events

Type of Event	Reporting Time Period: Consent to Randomization/Allocation	Reporting Time Period: Randomization/Allocation through Protocol-Specified Follow-up Period	Reporting Time Period: After the Protocol Specified Follow-up Period	Timeframe to Report Event and Follow-up Information to SPONSOR:
Non-Serious Adverse Event (NSAE)	Report if: - due to protocol-specified intervention - causes exclusion - participant is receiving placebo run-in or other run-in treatment	Report all	Not required	Per data entry guidelines

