### **9.10.3.1 Safety Follow-up Visit**

The mandatory Safety Follow-up Visit should be conducted approximately 30 days after the last dose of trial treatment or before the initiation of a new anticancer treatment, whichever comes first.

All AEs that occur prior to the Safety Follow-Up Visit should be recorded (up to 30 days following end of treatment). Participants with an AE of Grade >1 will be followed until the resolution of the AE to Grade 0 to 1 or until the beginning of a new anticancer therapy, whichever occurs first. SAEs that occur within 30 days (90 days following administration of pembrolizumab) of the end of treatment or before initiation of a new anticancer treatment should also be followed and recorded.

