### **9.10.3.2 Survival Follow-up Visits**

Participants, who experience confirmed disease progression or start a new anticancer therapy will move into the Survival Follow-Up Phase and should be contacted by telephone every 12 weeks to assess for survival status until death, withdrawal of consent, or the end of the study, whichever occurs first.

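### The schedule's last AE/SAE review falls on Day 23 to 37 after the last dose, while Sections 5.1.1 and 9.10.3.1 run AEs to Day 30 and SAEs to Day 90

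*Combined protocol and SAP*

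**What the plan says.** The SoA has two post-treatment columns. Safety Follow-up is set at "30 days after the last dose" with a window of ±7 days. Survival Follow-up is set at "Every 12 weeks after the last dose" with a window of ±14 days. The AE/SAE Review row is marked through treatment, at End of Treatment and at Safety Follow-up. It has no mark under Survival Follow-up.

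The text sets the periods as follows.

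- Section 5.1.1 on AEs: "All participants will be followed for at least 30 days after their last dose of MK-7162 for AE monitoring".
- Section 5.1.1 on SAEs: "Serious adverse events will be collected for 90 days after discontinuation". The period shortens to 30 days if new anticancer therapy starts before Day 30, or to the start date if therapy begins between Day 30 and Day 90.
- Section 9.10.3.1 on the visit: it "should be conducted approximately 30 days after the last dose of trial treatment or before the initiation of a new anticancer treatment, whichever comes first".
- Section 9.10.3.1 on recording: "All AEs that occur prior to the Safety Follow-Up Visit should be recorded (up to 30 days following end of treatment". SAEs run to 30 days, or to 90 days following pembrolizumab, or until new anticancer treatment.
- Section 9.3.1, to which the synopsis refers for post-treatment AE follow-up, requires reporting of all AEs and SAEs for only 14 days after treatment stops. Beyond that, only drug-related SAEs that come to the investigator's notice are reportable.
- Section 9.10.3.2: participants with confirmed progression or new anticancer therapy "should be contacted by telephone every 12 weeks to assess for survival status".
- Section 9.2.4: participants who stop without progression continue imaging every 9 weeks.

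**The concern.** A site that follows the SoA exactly can hold its last scheduled AE/SAE review a week before the 30-day AE period ends. It then has no scheduled occasion to ask about new SAEs for most of a 90-day period. AEs are a primary endpoint, and Sections 7.2.4 and 7.2.4.2.1 warn that immune-related events can appear months after treatment has ended. An event first arising after the Safety Follow-up visit would depend on the participant, another clinician or an incidental contact bringing it to the site.

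At stake is how completely post-treatment AEs and SAEs are recorded, and so the late-toxicity evidence that enters the overall safety picture. The group most exposed is participants who stop without progression and take no new therapy, for example because of toxicity or after 36 cycles. Their SAE period stays open to Day 90 under Section 5.1.1, yet they receive no survival calls.

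**Working it through.** The plan gives no figure for this gap, so there is none to reproduce. The check is calendar arithmetic.

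**Inputs.** Safety Follow-up at Day 30 ±7 (SoA). AE period of 30 days (5.1.1, 9.10.3.1). SAE period of 90 days (5.1.1, 9.10.3.1). Reporting period of 14 days (9.3.1). Survival contacts every 12 weeks ±14 days (SoA).

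**Step 1, allowed visit days.** 30 − 7 = 23 and 30 + 7 = 37, so Day 23 to Day 37. An earlier visit is allowed only when new anticancer treatment starts sooner; that case is left out below.

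**Step 2, days with no scheduled AE/SAE review.** Gap = end of period − visit day, or 0 if negative.

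| Period | Visit Day 23 | Visit Day 30 | Visit Day 37 |
|---|---|---|---|
| 14 days (9.3.1) | 0 | 0 | 0 |
| AE, 30 days | 7 | 0 | 0 |
| SAE, 90 days | 67 | 60 | 53 |

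As shares, 7/30 = 23% of the AE period at worst. For SAEs the shares are 67/90 = 74%, 60/90 = 67% and 53/90 = 59%.

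**Step 3, first survival call.** 12 × 7 = 84, 84 − 14 = 70 and 84 + 14 = 98. A call may fall 20 days before Day 90 (on Day 70), 6 days before it (on Day 84), or after it. Only a call on Day 90 to 98 could cover the full SAE period, and none is marked for AE/SAE review.

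**Step 4, contacts each group has after the visit.**

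- Confirmed progression, no new therapy: survival calls, with the SAE period open to Day 90.
- New therapy between the visit and Day 90: survival calls, with the SAE period ending when that therapy starts. The gap is shorter, from the visit to that date.
- Neither progression nor new therapy: no survival calls, only 9-weekly imaging without an AE review mark. The full gap applies under Section 5.1.1.

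**Step 5, starting points.** The table counts every period from one day. The documents count variously from the last dose, discontinuation, end of treatment and pembrolizumab administration. If 90 days run from the last infusion, and that infusion was given on schedule up to 20 days before the last MK-7162 dose, the period ends as early as 90 − 20 = Day 70 after the last dose. The gaps are then 70 − 23 = 47, 70 − 30 = 40 and 70 − 37 = 33 days. A participant who stops in Cycle 1 has had no pembrolizumab, so falls under 30 days in Section 9.10.3.1 but 90 days in Section 5.1.1.

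**The case against.** The strongest reply is that a visit window says when a visit may happen and does not close data collection. Section 5.1.1 sets 30 days independently of the visit, and Section 9.10.3.1 also names 30 days. Investigators are responsible for detecting events (9.3), open-ended questioning is the preferred method (9.3.2), and Table 8 requires all SAEs to be reported through the protocol-specified follow-up. Section 7.7.1 expects medications for SAEs to be recorded beyond 30 days. This stands in part: a Day 23 visit does not formally shorten the AE period. But these are general duties, and none schedules an occasion to ask. Section 9.3.3 requires proactive follow-up only of events already reported.

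A reader might infer that contact stops after the visit. It does not. Survival calls, 9-weekly imaging and follow-up of ongoing events above Grade 1 continue, and the later contacts also record new anticancer therapy. What ends is the scheduled AE/SAE review.

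A reader might also take Section 9.3.1 as waiving active questioning in this interval: "Investigators are not obligated to actively seek AE or SAE or other reportable safety events in former study participants". That sentence concerns former participants, and Section 8.1 keeps people who stop treatment in the study. Section 5.1.1, however, describes them as discontinued from the study once treatment ends, so sites could read it either way. It is not firm support for the point.

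Finally, against the 14-day period of Section 9.3.1 there is no gap at all. That is correct, and it is why reconciliation comes first. It does not dispose of the point: if the 30/90-day text is kept, the SoA still does not implement it.

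**Conclusion.** The point holds as a mismatch between the SoA and the 30/90-day text. Up to 7 days of the AE period, and 53 to 67 days of the SAE period, have no scheduled AE/SAE question. The SAE figures are for a participant whose 90-day period is not cut short by new therapy, with all periods counted from the same day. They also assume that the AE/SAE Review row has no mark under Survival Follow-up. That should be confirmed on the formatted table, because the row's treatment cells are merged under an arrow. Its post-treatment marks sit in the same cells as those of Full Physical Examination, which makes a survival-call mark implausible.

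Two stronger conclusions are not supported.

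- **A missed share of SAEs.** If SAEs are spread evenly and passive capture after Day 30 is 25% to 75%, then 60/90 × (1 − capture) gives 50% to 17% missed. Neither input is in the documents, so the result only restates the assumptions.
- **A biased dose recommendation.** The mTPI decisions and DLT-rate estimates use the first 42 days from first dose and are not affected. Late events can enter only through the overall weighing of safety data, and nothing shows that they would change the choice.

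What remains is an inexpensive improvement in ascertaining a primary safety endpoint.

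**What to change.** 1. Reconcile the 14-day text of Section 9.3.1 with the 30- and 90-day text of Sections 5.1.1 and 9.10.3.1, and give each period one starting point.
2. If 30 and 90 days are kept, change the Safety Follow-up window in the SoA from ±7 days to 0 to +7 days, keeping the exception for an earlier start of new anticancer therapy.
3. Mark AE/SAE Review for one contact at or shortly after Day 90 for each participant whose SAE period is still open, covering the whole interval since the Safety Follow-up visit. Where a first 12-week call is already due, hold it on Day 90 to 98, inside its existing window of Day 70 to 98. Others need one added telephone call. For participants who started new therapy after the visit, the first survival call could also ask about the interval up to that start without a further contact.

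The cost is SoA wording and at most one short call per participant, about 40 in Part A. The change concerns data collection only.
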